#### 9.1.4. Secondary endpoints

- MRD Negativity following initiation of Ino
- Number of cycles of InO needed to attain CR/CRi
- DOR
- Dosage pattern: InO doses, dose modifications, and the number of cycles of treatment;
- Concomitant medications
- Rate of transplant (No of patients who proceeded to transplant)
- Survival rate at 6 months & 12 months (transplanted patients & non transplanted patients, in both who achieved CR/CRi and MRD negativity)
- Cause of death
- Relapse-free-survival; in all patients and patients with or without follow-up HSCT.
- Rate of VOD (Total, during study treatment and post HSCT, if any patient underwent HSCT) in transplanted & non transplanted patients.
- Occurrence of Grade 3/4 treatment-related adverse events in lung/cardiac/kidney/liver etc following InO initiation; in all patients and patients with or without follow-up HSCT & hematological toxicities
- CR/CRi in EMD/LBL

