#### 9.5. Data analysis

All qualitative outcomes will be summarized by frequency and percentage. The quantitative outcome will be summarized by mean and SD if data is symmetric, otherwise median, and IQR. The outcomes will also be classified and compared across different demographic and relevant clinical factors. External validity will be assessed by t-test/ANOVA or chi-square test of indepdence depending on the nature of the outcome. However, observations will be generalized for the population the selected patients would represent. p-value<0.05 will be considered statistical significance. A standard statistical software will be used for data analysis.

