# 11. MANAGEMENT AND REPORTING OF ADVERSE EVENTS/ADVERSE REACTIONS

- All AEs will be captured from the medical records.
- Number of Participants Who Experienced a Documented Diagnosis of Veno-occlusive Disease (VOD)/Sinusoidal Obstruction Syndrome (SOS) Post InO Treatment.
- Number of Participants Who Survived Following Treatment For Documented Diagnoses of Venoocclusive Disease (VOD)/Sinusoidal Obstruction Syndrome (SOS).
- Number of Participants With Interrupted InO Treatment Due to VOD/SOS.
- Number of Participants Who Experienced Grade 3 and Grade 4 (Lung/Cardiac/Kidney/Liver) Treatment-Related Adverse Event (TRAE) Following InO initiation.
- All hematological AEs: Neutropenia, febrile neutropenia, and thrombocytopenia
- Being NIS secondary data collection— This study involves retrospective patients treated with InO for R/RB-cell ALL data that exist as unstructured data by the time of study start or a combination of existing unstructured data, which will be converted to structured form during the implementation of the protocol solely in an excel using CRF template.
- It is not possible to link (ie, identify a potential association between) a particular product and medical event for any individual. Thus, the minimum criteria for reporting an AE (ie, identifiable patient, identifiable reporter, a suspect product, and event) cannot be met.

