# 7.2.2 Analyses of endpoint

The following tables and figures will be generated for the analysis of endpoints.

- 1. The distribution of demographics characteristics (mean ±SD for age and frequency and percentage for sex)
- 2. MRD negativity following initiation of InO (frequency and percentage)
- 3. Dosage pattern (frequency and percentage)
- 4. Cause of death (frequency and percentage)
- 5. Occurrence of Grade 3/4 treatment-related adverse events in lung/cardiac/kidney/liver etcfollowing InO initiation (frequency and percentage)
- 6. CR/CRi in EMD/LBL (frequency and percentage)
- 7. Duration of response (DOR) (Median and Interquartile Range (IQR))
- 8. No of patients who proceeded to transplant (Median and IQR)
- 9. Total during study treatment and post HSCT (Median and IQR)
- 10. Restricted remission free time with 95% confidence interval for both complete remission and complete remission with incomplete hematological recovery.

- 11. Restricted remission free time with 95% confidence interval for both complete remission and complete remission with incomplete hematological recovery stratified by the number of salvage therapies  $(0, 1, \ge 2)$  received before InO initiation
- 12. Restricted mean overall survival time with 95% CI.
- 13. Restricted relapse-free-survival with 95% CI for all patients and patients with or without follow-up HSCT.

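### Grade 3/4 organ events have no end of window and no attribution rule, and the SAP outputs lose the separate VOD windows, so crude harm rates by HSCT status are not comparable

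*Protocol*

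**What the plan says.** **Organ toxicity.** Protocol 9.1.4, repeated in SAP 5, lists "Occurrence of Grade 3/4 treatment-related adverse events in lung/cardiac/kidney/liver etc following InO initiation", with timing and grouping given as "following InO initiation; in all patients and patients with or without follow-up HSCT & hematological toxicities". The count starts at InO initiation. No end is stated.

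**VOD.** Protocol 9.1.4 asks for "Rate of VOD (Total, during study treatment and post HSCT, if any patient underwent HSCT) in transplanted & non transplanted patients". Protocol 9.1 and SAP 5 have the same three-part wording. Protocol 11 adds a count, "Number of Participants Who Experienced a Documented Diagnosis of Veno-occlusive Disease (VOD)/Sinusoidal Obstruction Syndrome (SOS) Post InO Treatment", with no end date and no HSCT split.

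**SAP outputs.** SAP 2.1 and 2.2 drop the comma after the word total, so the three readings become one. SAP 7.2, 7.2.2 (item 9) and 8 (item 9) also drop the word VOD, leaving "Total during study treatment and post HSCT (Median and IQR". Item 5 is a single frequency table of Grade 3/4 events with no HSCT split. SAP 5.2 and 7.2.1 mark safety endpoints and safety analyses as not applicable, and Appendix A1.2 gives no further endpoint definitions.

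**Attribution.** Protocol 11 states: "It is not possible to link (ie, identify a potential association between) a particular product and medical event for any individual". Item 5 of the administrative change letter moves that paragraph under a structured-data heading in Section 12 and says it is revised. Protocol 12 requires an explicit causality statement by a healthcare provider, but for safety reporting, not for this endpoint.

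**Comparison.** Protocol 9.5 says: "The outcomes will also be classified and compared across different demographic and relevant clinical factors". It does not name HSCT status. The SAP has no hypothesis (3.1) and limits interpretation to a qualitative sense (7.2).

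**The concern.** HSCT happens after the index date, and a patient must survive InO treatment to reach it. Only recipients can contribute time after HSCT. An organ-event count with no end therefore takes in the transplant period for one group and some other post-InO period for the other. The VOD total does the same by design.

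A reader of such a table could not tell whether a difference between the groups reflects InO, the transplant, the length of observation or who lived to be transplanted. The all-patient total has a related problem: it can move with the share transplanted even if toxicity on InO is constant. That matters when Protocol 9.1.4 applies every parameter to subgroups whose transplant shares may differ.

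The on-treatment VOD rate is the figure that would escape most of this. The protocol asks for it, but no SAP output delivers it as n/N.

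**Working it through.** The documents give no VOD rate, toxicity rate, risk window or planned HSCT share, so there is no figure to reproduce. The texts are set side by side first; the arithmetic after that is illustration.

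**1. Endpoint against output**

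| Item | Protocol 9.1.4 and SAP 5 | SAP 7.2.2 and 8 |
|---|---|---|
| VOD windows | total; during treatment; after HSCT | one item, periods run together |
| VOD named | yes | no (item 9) |
| VOD summary | rate | median and IQR |
| Organ events by HSCT | yes | no split (item 5) |
| End of organ-event window | none | none |
| Rule for treatment-related | none | none |

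The nearest thing to a limit is the 6 months or 1 year in Protocol 9.2. That wording attaches to OS, the SAP data-source section replaces it with death or data retrieval, and one year would still include time after HSCT. SAP 5.1 takes the study period as the longest time from InO start to data extraction. With initiation from February 2017 to February 2022 and data collection ending in July 2023 (change letter), potential follow-up is about 17 to 77 months.

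**2. What pooling can do to the VOD total**

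Assumptions: on-treatment risk p is the same in both groups, there is a further risk q after HSCT in recipients, and others have no late VOD. Recipients' total = 1 − (1 − p)(1 − q); others' total = p.

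| p (others' total) | q = 5% | q = 10% | q = 20% | q = 30% |
|---|---|---|---|---|
| 2% | 6.9% | 11.8% | 21.6% | 31.4% |
| 5% | 9.8% | 14.5% | 24.0% | 33.5% |
| 10% | 14.5% | 19.0% | 28.0% | 37.0% |

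The gap, (1 − p)q, runs from 0.90 × 5% = 4.5 points to 0.98 × 30% = 29.4 points. The ratio runs from 14.5/10 = 1.45 to 31.4/2 = 15.7. With q = 0 there is no gap.

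For the all-patient total, take 32 patients (change letter) and, purely as an illustration, the 41% HSCT share of the phase 3 trial cited in Protocol 7: 32 × 0.41 = 13.1, so 13 recipients and 19 others. With p = 5% and q = 10%, expected VOD is 13 × 0.145 + 19 × 0.05 = 2.835, or 8.9% of 32, against 5.0% on treatment. Of that, 13 × 0.095 = 1.235 (44%) arises after HSCT.

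**3. Why the direction is not known**

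Let non-transplanted patients have late VOD risk r. The gap becomes (1 − p)(q − r). With p = 5% and q = 10%: r = 0 gives +9.5 points, r = 10% gives 0, and r = 20% gives −9.5 points. The table in step 2 is the r = 0 case only.

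**4. Organ events with an open window**

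Assume a constant 2% per month in both groups, with risk = 1 − exp(−rate × months). Twelve months at risk gives 1 − exp(−0.24) = 21.3%; six months gives 1 − exp(−0.12) = 11.3%. Unequal observation alone nearly doubles the crude proportion. Which group is observed longer is not stated.

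**5. Precision**

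With 13 and 19 patients, 3/13 has an exact 95% CI of 5.0% to 53.8%, and 1/19 has 0.1% to 26.0%.

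**The case against.** The strongest defence is that the protocol already separates the VOD windows. Protocol 9.1, 9.1.4 and SAP 5 all ask for the on-treatment and post-HSCT readings alongside the total, and the on-treatment reading covers the same phase in both groups. Item 9 may be a garbled title, not a decision to pool. This stands: only the total mixes windows, and the SAP needs to restore what the protocol requests. On-treatment VOD split by later HSCT would still group patients by a future event.

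A reader might infer that the plan counts transplant harm as InO harm. The documents do not say that. The organ endpoint is limited to treatment-related events, and post-HSCT VOD has its own reading. What is missing is the rule that would make the limit work, since Protocol 11 and 12 point in different directions on attribution and neither is written for this endpoint.

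A reader might also infer that transplanted patients must show the higher rate. That does not follow. Neither group has a stated end of window, non-transplanted patients are followed after InO too, and every risk in the illustration is assumed.

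Nor does the plan specify a formal test of harm by HSCT status. HSCT is not among the listed subgroups, item 5 has no HSCT split, and interpretation is qualitative. The missing split in item 5, however, leaves a stated endpoint undelivered; it does not resolve the window problem. Finally, the not-applicable entries in SAP 5.2 and 7.2.1 do not remove these events, which remain in SAP 5, 7.2 and item 5.

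**Conclusion.** The point holds in limited form. Crude organ-event rates and VOD totals by HSCT status are not comparable under the plan as written, and InO-period harm cannot be separated from post-transplant harm in the SAP outputs. This rests on the text alone: no end of window, no attribution rule for the endpoint, a split on a post-index event, and a VOD output that has lost its windows, its name and its proper summary measure.

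The size and direction cannot be established. The gaps of 4.5 to 29.4 points assume equal on-treatment risk of 2% to 10%, post-HSCT risk of 5% to 30%, and no late VOD in non-transplanted patients; relaxing the last assumption can remove or reverse them. In a descriptive study of 32 patients this is an inexpensive improvement to the safety tables. It does not affect the primary endpoint.

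**What to change.** In Protocol 9.1.4 and SAP 5, 7.2, 7.2.2 (items 5 and 9) and 8, tabulate VOD and Grade 3/4 organ events as n/N with 95% CI in two windows:

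- **On InO:** onset from the index date to the earliest of HSCT, next anti-leukaemic therapy, or a fixed number of days after the last InO dose that the sponsor defines. Denominator: all patients.
- **After HSCT:** onset on or after the HSCT date, which is time zero. Denominator: recipients only.

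Add one row for later events in never-transplanted patients and one for events with unknown onset date, so that none is lost. Name VOD in item 9 and remove the median and IQR.

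State how treatment-related is determined for this endpoint, and reconcile Protocol 11 (as revised by the change letter) with Protocol 12. If a total by HSCT status is kept, label it as covering different observation periods and do not present it as a comparison.

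Cost: wording in both documents, one reorganised table and a less prominent HSCT contrast. It depends on onset, last-dose and HSCT dates being in the charts, which the documents do not confirm.

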#### All these parameters will be assessed in the following subgroups -

- 1st salvage and later lines
- High burden and Low burden disease (<50%; 50-90%; >90%)
- Ph +ve and Ph ve patients
- Elderly patients> 65 years

#### 9.2. Data sources

Data for this study will be collected through retrospective data collection from 7-10 sites for patients in India who received Inotuzumab for the indication of adult R/R B Cell ALL between the time period Feb'2017 – Feb'2022. Additional centers may be added at a later stage if the target sample size is not achieved.

Data will be collected in anonymized form on Paper/excel based CRF for the study. Participants will be identified in all study records by a unique participant identification number to allow data management queries to be resolved with reference to source medical records while preserving patient confidentiality.

Medical records will be reviewed from secondary data sources to collect demographic, patientrelated, disease-related, and clinical outcome data & AE's. These patients will be evaluated for response, duration of response (DOR), OS from the time of InO initiation till 6 months or 1 year of therapy and toxicity

Data to be verified in accordance with Protocol standards. Before obtaining the data from the selected sites across the nation, the necessary regulatory approval will be ensured.

#### 9.3. Study size

This is a descriptive study and there is no prior hypothesis specified, therefore a formal power calculation is not required. The sample size of approximately 55 patients has been based on the number of patients expected to be available at these 7-10 sites that individually treated the largest number of patients with InO

The study will include information on approximately 55 patients as per the availability of data from 7-10 sites.

#### 9.4. Data management

## 9.4.1. Collection, Monitoring, Processing of Data and Archiving:

Data pertaining to all fields required to fulfill the primary and secondary endpoints of the study will be captured in a paper Case Report Form (CRF). Data from the paper CRF will then be transferred to an excel master managed by Insignia. Data entry, data query generation & resolution, source document verification & database lock will be performed as per standard GCP guidelines. **Rules for completing CRFs** 

Print legibly using preferably a black/blue ballpoint pen. Ensure that all questions are answered and that no empty data blocks exist. Ensure that no information is recorded outside the data blocks. If the question is irrelevant (eg, is not applicable) indicate this by writing "NA" (not applicable) in the respective ensure that all information derived from source documentation is consistent with the source information. By signing the affirmation statement, the Investigator confirms that the information answer field.

The investigator staff must is complete and correct.

## **Corrections to CRFs:**

Corrections to the data on the CRFs must only be made by drawing a straight line through the incorrect data and by writing the correct value next to data that has been crossed out. Each correction must be initialed, dated and explained by the Investigator or the Investigator's authorised staff.

#### **Monitoring of CRFs:**

Filled case report forms will be checked for accuracy by designated staff before sending them to Insignia for data entry, validation and analysis. The case report forms will be checked and collected in a mutually agreed frequency. Investigator will be responsible for the retention of patient notes for 1 year from the study closeout

#### 9.4.2. Case report forms (CRFs)/Data collection tools (DCTs)

As used in this protocol, the term CRF should be understood paper-based case report form for the data collection method used in this study.

A CRF is required and should be completed for each included patient. The completed original CRFs are the sole property of Pfizer and should not be made available in any form to third parties, except for authorized representatives of Pfizer or appropriate regulatory authorities, without written permission from Pfizer. The investigator shall ensure that the CRFs are securely stored at the study site in paper case report form and will be password protected or secured in a locked room to prevent access by unauthorized third parties.

The investigator has ultimate responsibility for the collection and reporting of all clinical, safety, and laboratory data entered on the CRFs-and any other data collection forms (source documents) and ensuring that they are accurate, authentic/original, attributable, complete, consistent, legible, timely (contemporaneous), enduring, and available when required. The CRFs-must be signed by the investigator or by an authorized staff member to attest that the data contained on the CRFs are true. Any corrections to entries made in the CRFs or source documents must be dated, initialed, and explained (if necessary) and should not obscure the original entry.

The source documents are the hospital or the physician's chart. In these cases, data collected on the CRFs-must match those charts.

#### 9.4.3. Record Retention

To enable evaluations and/or inspections/audits from regulatory authorities or Pfizer, the investigator agrees to keep records, including the identity of all participating patients (sufficient information to link records, e.g., CRFs and hospital records), copies of all CRFs7 safety reporting forms, source documents, detailed records of treatment disposition, and adequate documentation of relevant correspondence (e.g., letters, meeting minutes, and telephone call reports). The records should be retained by the investigator according to local regulations or as specified in the clinical study agreement (CSA), whichever is longer. The investigator must ensure that the records continue to be stored securely for as long as they are retained.

If the investigator becomes unable for any reason to continue to retain study records for the required period (e.g., retirement, relocation), Pfizer should be prospectively notified. The study

#### PFIZER CONFIDENTIAL

CT24-WI-GL02-RF02 4.0 Non-Interventional Study Protocol Template For Secondary Data Collection Study 01-Jun-2022 Page 17 of 24 records must be transferred to a designee acceptable to Pfizer, such as another investigator, another institution, or an independent third party arranged by Pfizer.

Study records must be kept for a minimum of 15 years after completion or discontinuation of the study, unless Insignia Communications Pvt Ltd and Pfizer have expressly agreed to a different period of retention via a separate written agreement. Record must be retained for longer than 5 years or as required by applicable local regulations.

The investigator & Insignia Communications must obtain Pfizer's written permission before disposing of any records, even if retention requirements have been met.

#### 9.5. Data analysis

All qualitative outcomes will be summarized by frequency and percentage. The quantitative outcome will be summarized by mean and SD if data is symmetric, otherwise median, and IQR. The outcomes will also be classified and compared across different demographic and relevant clinical factors. External validity will be assessed by t-test/ANOVA or chi-square test of indepdence depending on the nature of the outcome. However, observations will be generalized for the population the selected patients would represent. p-value<0.05 will be considered statistical significance. A standard statistical software will be used for data analysis.

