# 3 HYPOTHESES AND DECISION RULES None

# **3.1 STATISTICAL HYPOTHESES**

This is a descriptive study and there is no prior hypothesis specified. The objective of this study is just to observe clinical outcomes among patients treated with InO monotherapy in real-world clinical practice in India.

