# 3.2 STATISTICAL DECISION RULES

As no specified hypothesis will be tested, no decision rule are required to specify. However, for any assessment of external validity for a suitable population accepted false positive rate will be 5%. For any such validation only two sided test will be performed.

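### t-tests, ANOVA and chi-square tests at p<0.05 are assigned to assess external validity, but with no outside reference they can only compare subgroups of the same 32 patients

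*Protocol*

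**What the plan says.** Protocol 9.5 first sets up comparisons inside the cohort: "The outcomes will also be classified and compared across different demographic and relevant clinical factors". The next sentence gives the purpose and the method: "External validity will be assessed by t-test/ANOVA or chi-square test of indepdence depending on the nature of the outcome". The section then sets an unqualified threshold: "p-value<0.05 will be considered statistical significance".

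Both documents disclaim testing. Protocol 9.3 says: "This is a descriptive study and there is no prior hypothesis specified, therefore a formal power calculation is not required". SAP 3.1 says: "This is a descriptive study and there is no prior hypothesis specified". SAP 3.2 begins: "As no specified hypothesis will be tested, no decision rule are required to specify". It then makes an exception: "for any assessment of external validity for a suitable population accepted false positive rate will be 5" per cent, followed by "For any such validation only two sided test will be performed".

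No outside reference is supplied. SAP 2.1 (treatment/cohort labels) says there is no other group, and SAP 4.3 says no other data set will be used. The suitable population mentioned in SAP 3.2 is never identified.

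SAP 7.1, 7.2 and the table list in section 8 contain no t-test, ANOVA, chi-square or external-validity output. On generalisability, SAP 7.2 restricts extrapolation to patients who match the sample, because sampling is non-probability, and ranks magnitude above statistical interpretation.

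**The concern.** External validity asks whether results carry over to patients outside the sample. A t-test, ANOVA or chi-square test of independence asks whether an outcome differs between groups that are both in the data. With no outside group or reference value, neither result of such a test bears on the first question. A significant result shows heterogeneity among the included patients. A non-significant one shows little at this sample size.

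At stake is a set of p-values reported under a heading they cannot support, in a study that says it tests no hypothesis. Protocol 9.6.2 obliges the data to be analysed and reported as the protocol describes, so the sentence in 9.5 is binding even though the SAP specifies no analysis to carry it out.

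**Working it through.** **Nothing to reproduce.** The plan's only figure on this point is the significance level, 0.05 in both documents. No effect size or power is stated, and the sample size rests on availability.

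**Inputs.**
- N = 32, from item 4 of the administrative change letter. Protocol 9.3 and the SAP carry about 55, which is used below as a sensitivity check.
- 81% response, the InO arm of the phase 3 trial quoted in protocol section 7, used as an illustrative rate.
- Assumptions: two subgroups of 16, a target-population rate of 60%, and the other response rates shown.

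**Test used.** Pearson chi-square for two groups of size n₁ and n₂: z = (a/n₁ − b/n₂) / √[p̄(1 − p̄)(1/n₁ + 1/n₂)], where a and b are the responders and p̄ = (a + b)/(n₁ + n₂). It rejects when |z| > 1.96. The rejection probability is the sum of the binomial probabilities of all (a, b) that reject. The target population's rate does not appear anywhere in the formula.

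**Check 1: does the test notice an unrepresentative sample?** Both halves of the sample share one rate, and the target rate is 60%.

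| Sample rate, both halves | Distance from target | Rejects, 16 vs 16 |
|---|---|---|
| 50% | −10 points | 5.2% |
| 60% | 0 | 5.3% |
| 70% | +10 points | 5.7% |
| 81% | +21 points | 5.2% |

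The rejection rate stays close to the nominal 5% whether the bias is zero or 21 points. At N = 55 (27 vs 28) it is 4.8% to 5.8%.

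**Check 2: can it reject when the sample is representative?** Take a faithful sample of a population whose two subgroups truly respond at 81% and 40%. The test rejects 69.5% of the time at 16 vs 16, and 90% at N = 55.

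**Check 3: what does a null result tell us?** Rejection probability at 16 vs 16:

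| True rates (assumed) | Gap | Rejects |
|---|---|---|
| 81% vs 60% | 21 points | 28% |
| 90% vs 70% | 20 points | 30% |
| 81% vs 50% | 31 points | 48% |
| 90% vs 50% | 40 points | 76% |

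**Check 4: are the cells large enough for chi-square?** With 81% response and three equal salvage strata, expected non-responders per stratum are 32 × 0.19 / 3 = 2.0, below the usual minimum of 5. At N = 55 the figure is 55 × 0.19 / 3 = 3.5.

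**Check 5: multiplicity, as an illustration.** Protocol 9.1.3 and 9.1.4 list 1 + 12 = 13 endpoints, to be assessed in four subgroup factors. One test each gives 13 × 4 = 52 tests, with 52 × 0.05 = 2.6 false positives expected if no true differences exist. If the tests were independent, the chance of at least one is 1 − 0.95⁵² = 93%.

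**What estimates would show instead.** With 26 of 32 responding (81%), the exact 95% interval is 64% to 93%. In a stratum with 9 of 11 responding it is 48% to 98%.

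**The case against.** The strongest reply is that this is a wording fault with little consequence. SAP 7.2 already limits extrapolation, puts magnitude first and asks for qualitative interpretation. SAP 3.2 presents its 5% level as an exception, and nominal p-values in a descriptive study are not contradictory in themselves. The primary output is an estimate with a confidence interval. All of this stands, and it limits the severity.

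It can also be said that within-sample testing is an inference, since SAP 3.2 speaks of a suitable population and 4.3 does not clearly exclude published reference values. That is fair. However, a chi-square test of independence takes no external reference value, and none is supplied. Comparison within the cohort is the only reading the documents support.

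Three stronger readings are tempting and should not be drawn:

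- **A null result will be declared proof of external validity.** Neither document says so, and no rule for reading the result is given. The power figures show only that a null result is uninformative.
- **52 tests are planned, with a 93% chance of a false positive.** The SAP lists no p-value output, and SAP 4.4 makes subgroup analysis conditional on adequate numbers. Some listed endpoints, such as concomitant medications and cause of death, do not yield a single test. Independence is implausible for endpoints measured in the same patients.
- **Censored survival times will be analysed by t-test or ANOVA.** Protocol 9.7 assigns Kaplan-Meier estimation to OS, RFS and time to CR/CRi, and SAP 7.1 and 7.2 use Kaplan-Meier curves or restricted mean times. The exception is DOR, which is summarised by median and IQR with no stated method for censoring. No text assigns it a t-test either.

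**Conclusion.** The point holds. Protocol 9.5, echoed in SAP 3.2, gives these tests a task they cannot perform, because nothing outside the cohort enters them. This follows from the form of the tests and the absence of any named reference. It does not depend on the assumed rates, and it is the same at 32 or 55 patients.

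The figures show the size under stated assumptions. Rejection is about 5% to 6% whatever the bias, for equal rates in halves of 16, and about 70% in a representative sample with subgroup rates of 81% and 40%. The power range of 28% to 76% and the multiplicity figures are illustrations only.

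Severity is minor to moderate. The rule is wrong and should be corrected, but the primary CR/CRi estimate is unaffected and SAP 7.2 already restrains the conclusions.

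**What to change.** 1. In protocol 9.5, delete the sentence on testing external validity and the unqualified p<0.05 threshold. In SAP 3.2, delete the 5% rule for external validity.
2. Align protocol 9.5 with SAP 7.2, so that both restrict extrapolation to patients who match the sample.
3. Address generalisability by description: tabulate baseline characteristics such as age, Ph status, prior salvage, disease burden and access route, beside published phase 3 characteristics where these are available.
4. Report subgroup outcomes as estimates with exact 95% confidence intervals.
5. If any between-subgroup test of proportions is kept, label it exploratory and use an exact test (Fisher-Freeman-Halton for three strata), given about 2 expected non-responders per salvage stratum.
6. State how censored durations are handled in the DOR summary.

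The cost is wording in a few sections and the loss of nominal p-values. No additional patient data are needed for the deletions, and the analysis work falls slightly.
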